For data collection, participants may find thinking about thoughts and feelings that arise or answering questions about these issues upsetting; these questions will be asked in as sensitive a manner as possible. As well, if a participant answers no to a sexual activity question, they would not receive additional, more details questions about sex. By tailoring the questions, we minimize the exposure to sensitive questions and reduce the burden and fatigue that may arise from taking a survey. We use ACASI computer-based surveys to allow participants to read and answer the questions privately and not have to hear them aloud or tell another person, which may reduce any possible distress associated with answering the questions. While participants will be assured that their participation will not affect health and social services being provided at any location, some participants may feel concerned about or pressured to be part of the study. We will verbally assure participants at the beginning of each NCM session and at each follow-up that their participation is voluntary and that they can participate in all, part of, or none of the session and can withdraw from the study at any time for any reason without penalty. Another potential risk is the loss of confidentiality or disclosure of information or data about the participant. We have detailed below extensive measures to ensure confidentiality and decrease the risk for disclosure of private information.

During data collection, participants may refuse to answer any questions that make them feel uncomfortable. Participants may discontinue participation in the study at any time. We anticipate that the types of adverse experiences that may occur, if any, may be associated with issues

arising during data collection. None of these risks are considered significant. Having a study phone poses no more risk than having a personal phone.

This is a single site study.

Ongoing assessments that may impact safety or ethics of the study

The research team is active in HIV prevention research and will continue to monitor the literature, attend national and international conferences, and consult with colleagues to assure that we are aware of any emerging data that may impact safety or the ethics of the study.

Advanced plans for interim/futility analysis

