One focus of the investigator meetings will be to continuously monitor and develop strategies to prevent adverse reactions, monitor the research staff, and protect data integrity. Accrual data will be reviewed by the team and the UTHealth IRB. The study team will make amendments to the protocol should accrual fall below 15% of the target, or should drop-outs exceed projections by 15%. This will include the addition of recruitment sites.

Statistics

Randomization. Participants will be randomly assigned to the intervention or wait list control arm using a computer-generated blocked 2:1 allocation; 300 participants will be in the intervention arm and 150 will be in the wait list control arm (see Figure 3). Participants will be told which group they are in after completing the baseline survey and will receive a study-issued phone with programmed YEH resources unless they prefer to use their own phone. In this case, the behavioral feedback app will be loaded onto their personal phone for those in the intervention arm, and these youth will be provided with a list of YEH services.

Study Design.

| | Baseline | Intervention | 3 Mon. | 6 Mon. | 9 Mon. | Intervention |
|-------------------|----------------|------------------|----------------|----------------|----------------|--------------|
| Treatment arm | O ₁ | X O ₂ | O ₃ | O ₄ | O ₅ | |
| Wait list control | O ₁ | O ₂ | O ₃ | O ₄ | O ₅ | X |

Sample Size and Power Calculations. The primary endpoint is the efficacy of NCM to increase PrEP and nPEP uptake, HIV testing, STI screening, and condom use. Conservatively assuming an attrition rate of 30% at 9 months, the final sample size will be 315, with the 2:1 randomization allocation providing for 210 participants in the intervention arm and 105 in the control arm. We estimate a retention rate of 70% based on study resources, community partnerships and support, the use of study-issued phones, the use of increasing follow-up incentives. This retention rate is substantially lower than the rate reported for other longitudinal YEH studies that have retained 88-89% ^{13,14} of youth to be very conservative in our retention estimation.

Table1. Outcome Measures by Study Aim

| Construct | Scale/Measure | Alpha |
|-----------------------|---|-------|
| Aim 1 Outcomes | | |
| PrEP/nPEP Uptake | PrEP uptake; nPEP uptake (NCM report, chart review) | NA |
| Condom Use | Youth Risk Behavior Survey; ¹ (condom use at last sex) | NA |

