
instrument scores for the secondary outcomes including health seeking, coping, HIV/PrEP knowledge, and condom self-efficacy (see Table 2) will be examined as potential mediators in the path between the intervention and the outcome. Each of these indirect paths will be tested separately in multilevel (2-1-1) mediation models¹⁹ calculated in Mplus software.²⁰ The within-subject level in the mediating variable and the outcome (condomless sex) will be collapsed by taking the mean difference centered on each subject's baseline measurement. After collapsing the finest level, the intervention may be considered as a level 2 variable (i.e. between study arms) and the mediators and outcomes will be level 1 variables (subject-level).

Sex as a variable. In each of the analyses for Aims 1, 2, and the exploratory aim, we will assess for differences by sex (operationalized as gender identity, not biological sex). If the power is not adequate to assess for sex differences, we will control for sex differences in the analyses.

Equations for the models.

GEE models for aims 1 and 2 may be expressed as:

$$g(\mu_{ij}) = X_{ij}^k \beta^k,$$

where μ_{ij} is the mean response for subject i at time j , and g is a link function that is selected to be appropriate for the type of response variable (normal, binary, or Poisson). The predictors are denoted by X_{ij}^k , where the index k is used to distinguish between each predictor. The predictors include the study arm (control/treatment), the time, and the interaction of time and study arm. Covariates, such as sex, may be included if the randomization has not resulted in uniform distributions in each study arm. Solution of the GEE estimating equation will result in estimated values of the coefficients β^k .

Ethics

Adequacy of Protection Against Risks.

General Recruitment and Informed Consent.

Participant recruitment will begin after obtaining UTHealth IRB approval.

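### The exploratory mediation model uses the two study arms as its second level, which supports no arm-level standard error or test; low severity, corrected by rewording

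*Combined protocol and SAP*

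**What the plan says.** The Exploratory Aim paragraph of Analysis Plan by Study Aim (Statistics) gives the method: "Each of these indirect paths will be tested separately in multilevel (2-1-1) mediation models", to be run in Mplus. Before modelling, the repeated values of the mediator and of the outcome, given in brackets as condomless sex, "will be collapsed by taking the mean difference centered on each" subject's baseline value. The next sentence assigns the levels: "the intervention may be considered as a level 2 variable (i.e. between study arms) and the mediators and outcomes will be level 1 variables", with a bracket describing the level 1 variables as subject-level. No estimator for the standard errors is named.

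The candidate mediators are introduced as "instrument scores for the secondary outcomes including health seeking, coping, HIV/PrEP knowledge, and condom self-efficacy".

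The design offers no other grouping for level 2. Under Randomization, "Participants will be randomly assigned to the intervention or wait list control arm"; at the end of Potential Risks, "This is a single site study". The mediation paragraph does not mention nurse, shelter or recruitment location as a cluster.

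**The concern.** In a 2-1-1 model the exposure varies between level 2 units, and the mediator and outcome vary within them. This fits the trial if participants are level 2 and visits are level 1. The plan removes the visit level by collapsing it, then moves everything up one step: participants become level 1 and the arms become level 2. There are only two arms, and arm is also the exposure. The arm effect and any random arm-to-arm variation are then the same contrast, and the data cannot separate them.

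At stake is the standard error and test of each indirect effect. An analyst who follows the text could obtain different answers from different software settings, and the plan gives no basis for choosing among them.

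There is also a smaller consistency problem. HIV/PrEP knowledge is named as a mediator, but neither copy of the Outcome Measures by Study Aim table lists an instrument for it. It is also unclear whether mediation is planned for condomless sex alone or for every outcome in the Objectives.

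**Working it through.** **Inputs.** 450 randomised 2:1 (300 and 150), 30% attrition, 79% sexually active (Randomization; Sample Size and Power Calculations). Assumed here: normal scores with within-arm SD 1, and two-sided 5% tests. The documents give no sample size, power or standard error for mediation.

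**The plan's own figure.** 450 × 0.70 = 315; 300 × 0.70 = 210; 150 × 0.70 = 105. This reproduces "providing for 210 participants in the intervention arm and 105 in the control arm".

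**Degrees of freedom.** Level 2 units = 2. Level 2 fixed effects = 2 (intercept, arm). Residual df for path a (arm to mediator) = 2 - 2 = 0.

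**Arm-level variance.** Let τ be the between-arm SD. The estimate of path a is the difference in arm means whatever τ is, but its variance is 1/210 + 1/105 + 2τ².
- The maximum likelihood (ML) log-likelihood falls by ½[ln(1 + 210τ²) + ln(1 + 105τ²)], so it is highest at τ = 0, the single-level model.
- The restricted likelihood (REML) adds back exactly that amount, so it is flat in τ.

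One simulated data set (210 and 105, constants dropped) shows this:

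| τ | path a | SE(a) | ML | REML |
|---|---|---|---|---|
| 0 | 0.1413 | 0.1195 | -141.406 | -146.407 |
| 0.1 | 0.1413 | 0.1852 | -142.331 | -146.407 |
| 0.3 | 0.1413 | 0.4408 | -144.075 | -146.407 |
| 1 | 0.1413 | 1.4193 | -146.414 | -146.407 |
| 3 | 0.1413 | 4.2443 | -148.605 | -146.407 |

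The τ grid is illustrative; no conclusion rests on a non-zero value.

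**Arm-clustered robust standard error.** With arm in the model, residuals sum to zero within each arm, so both cluster scores are zero and SE(a) = 0. In simulation the largest value was about 5e-16, which is rounding error.

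**Mediator-to-outcome slope.** The design [1, arm, arm-mean mediator] has rank 2 of 3, so a between-arm slope cannot be told apart from the direct effect. The common-slope design [1, arm, mediator] has rank 3 of 3, so the within-arm slope can be estimated.

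**Illustration only.** With a true slope of zero at 210 versus 105, an arm-clustered robust test with a 1.96 cutoff rejects in 42% of simulated trials (32% with a G/(G-1) correction, G = 2 clusters), against 5.4% for the single-level test. Referred to t on 1 df (cutoff 12.71), the robust test rejects in about 8% and 5%. These runs were in Python, not Mplus.

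**Single-level model.** SE(a) = SD × √(1/n₁ + 1/n₀):
- 210 and 105: √(1/210 + 1/105) = 0.120 SD, 313 df.
- 300 and 150, if everyone contributes a follow-up: 0.100 SD, 448 df.
- 166 and 83 (0.79 × 210 and 0.79 × 105): 0.134 SD, 247 df.

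**Mediators and outcomes.** The mediation paragraph names four mediators, the Objectives five and the measures table six; none of the six is a knowledge measure. The Objectives list three outcome families, or four if PrEP and nPEP are separate as in the Aim 1 analysis. With five or six mediators that gives 5 × 3 = 15 to 6 × 3 = 18 models, or 5 × 4 = 20 to 6 × 4 = 24.

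**The case against.** The strongest reply is that maximum likelihood sets the arm variance to zero and gives the same answer as the proposed correction, so the second level is redundant rather than harmful. This is right about the numbers, and it is why the point is minor. But that route works only by discarding the level the plan describes, and the plan neither names maximum likelihood nor tells the analyst to drop the level.

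A second reply is that the level sentence is hedged and that participants are really meant as level 2. That would be a sound model, but the text collapses the visits and labels participants level 1, and it offers no other structure.

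A reader might infer from the 42% and 32% figures that the planned test has that error rate. The documents do not support this. The plan never proposes an arm-clustered robust standard error, and much of the inflation comes from the 1.96 cutoff. The figures show only how far the answer can move with the estimator.

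A reader might also see the shorter mediator list as contradicting the Objectives. That goes too far: the list is introduced as examples and refers to a table, and the same paragraph speaks of outcomes in the plural. The table reference does not settle the matter, since the table numbered 2 describes the intervention sessions. HIV/PrEP knowledge remains the one clear mismatch; the set of outcomes is merely unclear.

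**Conclusion.** The 2-1-1 structure is wrong as written. With two arms as level 2 there are 0 residual df for path a and no identifiable arm-level variance, so the second level adds nothing valid and the reported test depends on an unstated choice of estimator. This rests on individual randomisation to two arms, a single site and no other named cluster, all of which the documents state or imply. The df and identification results do not depend on the software; the simulated rates assume normal scores.

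It would be too strong to conclude that the mediation analysis cannot be done. Point estimates of path a and of the common within-arm slope are available and unaffected. Nor do the confirmatory results suffer: the GEE analyses for Aims 1 and 2 and the sample size do not use this model. Severity is low and confined to the exploratory aim.

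**What to change.** Delete the 2-1-1 label and the clause that makes arm a level 2 variable. State that, after collapsing, each participant contributes one mediator score and one outcome score, and that each indirect path is tested in a single-level mediation model with the participant as unit, arm as exposure, and a bootstrap interval that resamples participants within arm. Say how missed visits enter the collapsed mean.

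An equally acceptable alternative is to leave the visits uncollapsed, with visit as level 1 and participant as level 2. This keeps a genuine 2-1-1 model.

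Separately, name the HIV/PrEP knowledge instrument or drop that mediator, correct the table reference, and state whether the mediation outcomes are condomless sex only or all those in the Objectives. Label every model exploratory.

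The single-level version costs only wording: same data, same software, and unchanged maximum-likelihood point estimates. Some limits remain. Collapsed mediator and outcome cover the same visits, so temporal order is not established, and mediator-outcome confounding is not removed. Covering all the outcomes means 15 to 24 models. On the plan's own rates, PrEP models would have about 4 control events (0.04 × 105 = 4.2) against about 50 in the intervention arm (0.24 × 210 = 50.4).

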NCM4HIV capitalizes on the "come as you are" approach endorsed in the Clinical Guidelines⁷⁹ put forth by the National Healthcare for the Homeless Council (NHCHC) and aligns with NIH HIV/AIDS High Priority Research Area for reducing HIV through behavioral prevention and access to services in high HIV prevalence and substance-using populations. Additionally, NCM facilitates coordination with YEH service providers to meet mental health, substance use, and housing service needs and connects youth to the healthcare services at the Health Care for the Homeless Program (HCHP), such as HIV and STI testing and treatment. If efficacious, we will

partner with the NHCHC to disseminate the program across its approximately 300 programs and 3,300 clinics that provide care for people experiencing homelessness (see Letters of Support [LOS]).

Objectives

Aim 1: Determine whether the enhanced NCM intervention increases uptake of HIV prevention strategies (PrEP and nPEP uptake, HIV testing, STI screening and treatment, and condom use) when compared with wait list control youth (N=450; aged 16-25 years) at baseline, immediate post, and 3, 6, and 9 months

H1: Youth receiving NCM will have greater improvements in these outcomes over 9 months than control youth

Aim 2: Determine whether NCM4HIV improves mental health, substance use, and housing status when compared with wait list control youth at baseline, immediate post, and 3, 6, and 9 months

H2: Youth receiving NCM will have greater improvements in these outcomes over 9 months than control youth

[figure not shown]
Exploratory Aim: Determine if health seeking, coping, HIV risk perception, PrEP/nPEP barriers/facilitators, and condom self-efficacy mediate intervention effects on PrEP/nPEP uptake, HIV/STI testing, and condom use

Study Design

Figure 2. Study Design

| | Baseline | Intervention | 3 Mon. | 6 Mon. | 9 Mon. | Intervention |
|-------------------|----------------|------------------|----------------|----------------|----------------|--------------|
| Treatment arm | O ₁ | X O ₂ | O ₃ | O ₄ | O ₅ | |
| Wait list control | O ₁ | O ₂ | O ₃ | O ₄ | O ₅ | X |

Figure 3. Study Design

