Analysis Plan by Study Aim. Descriptive statistics will be calculated by study arm for baseline demographic characteristics, including age, gender identity, race/ethnicity, sexual orientation, educational level, and employment. However, random allocation of the participants to the intervention and control study arms will make it unlikely that there will be significant differences between the groups for baseline variables that could confound the results. Descriptive statistics will be calculated for all measures at each time point. We expect missing data to be minimal. Obvious errors will be corrected; those that cannot, will be set to missing. Missing data on the instruments will be replaced using single imputation with case mean substitution (i.e., replacing a participant's missing items with that participant's mean item score).¹⁶ Reliability estimates of the study instruments will be computed with Cronbach's alpha ($\geq .70$ will be considered acceptable for internal consistency).¹⁷ Analysis for this study will be based on the intent-to-treat principle.¹⁸ **Aim 1:** Generalized estimating equation (GEE) analysis will be used to compare the groups' changes over time in the dichotomous outcomes - PrEP uptake, nPEP uptake, condom use, and HIV/STI testing – assessed immediately post intervention and at 3-, 6-, and 9-months. The effects to be tested in the model will include time, study arm, and the interaction of time and study arm. **Aim 2:** GEE with normal distribution and identity link will be used to compare the intervention arm to the control arm over time with respect to mental health symptoms measured with the Brief Symptom Index, substance use, and number of homeless days in the past month. In case distributional assumptions are not met, Poisson link may be used for the number of homeless days and substance use days. The effects to be tested will include time, study arm, and the interaction of time and study arm. Time will be treated as a continuous variable unless nonlinearities are present, in which case it will be treated as a categorical variable. Hypothesis 1: Intervention youth will have increased PrEP/nPEP uptake and adherence, condom use, STI/HIV testing and treatment compared to wait list control youth. Hypothesis 2: YEH Intervention youth will have decreased mental health symptoms and substance use and report fewer nights on the street compared to waitlist control youth. **Exploratory Aim:** To explore for mediation of the variables in the Comprehensive Health Seeking and Coping Framework,

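### Covariate adjustment is optional and tied to chance imbalance, two rules for sex are not reconciled, and the role of the baseline outcome is unclear; a fixed baseline adjustment would be more precise for the arm effect

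*Combined protocol and SAP*

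**What the plan says.** Under Equations for the models, the default GEE terms for Aims 1 and 2 are set out: "The predictors include the study arm (control/treatment), the time, and the interaction of time and study arm". The text then adds: "Covariates, such as sex, may be included if the randomization has not resulted in uniform distributions in each study arm".

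Sex as a variable, just above, has a different rule. Differences by gender identity are to be assessed in every analysis, and "If the power is not adequate to assess for sex differences, we will control for sex differences in the analyses".

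The reasoning is in Analysis Plan by Study Aim: random allocation "will make it unlikely that there will be significant differences between the groups for baseline variables that could confound the results". That argument is about confounding; precision is not mentioned. Randomization describes a "computer-generated blocked 2:1 allocation; 300 participants will be in the intervention arm and 150 will be in the wait list control arm" and names no stratification factor.

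On the baseline outcome the text points two ways. Under Objectives, Aim 1 compares the arms ("N=450; aged 16-25 years) at baseline, immediate post, and 3, 6, and 9 months"). The Aim 1 sentence of the analysis plan speaks of changes over time but describes the outcomes as "assessed immediately post intervention and at 3-, 6-, and 9-months". The Aim 2 sentence gives no visit list.

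**The concern.** The first rule leaves four things open: which covariates are candidates, how non-uniformity is measured, whether adjustment then follows (the verb is permissive), and whether the adjusted or the unadjusted result is primary. All four can be settled once baseline data by arm, and possibly outcomes, are in hand.

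The trigger also looks at the wrong property. Under correct randomisation any imbalance is chance, and its size says nothing about whether the variable predicts the outcome. A strongly prognostic variable that happens to balance is left out, while a useless one that does not may be put in.

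At stake are a primary model that is not fixed in advance and precision that could be had from data already collected.

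**Working it through.** **1. The plan's own figures.** "Conservatively assuming an attrition rate of 30% at 9 months, the final sample size will be 315": 450 × (1 − 0.30) = 315, or 210 v 105. This reproduces. The stated interval for 87% power (84.8 to 89.0) is the exact binomial interval for 870/1000, so it reproduces too. The 87% itself can be neither confirmed nor refuted, because the within-person correlation, the shape over time and the tested term are not stated. The power text mentions no covariates.

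**2. The two sex rules side by side.**

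| Arms balanced on sex? | Power for sex differences? | Imbalance rule | Sex rule |
|---|---|---|---|
| Yes | Adequate | No reason to include | Assess differences |
| Yes | Inadequate | No reason to include | Control for sex |
| No | Adequate | May include | Assess differences |
| No | Inadequate | May include | Control for sex |

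In the second row one rule includes sex and the other gives no ground for it. In the fourth row one permits what the other requires. Neither has a threshold.

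**3. How often chance alone would trigger adjustment.** The plan names no test. Assume p < 0.05, independent variables, and all six demographics listed for description as candidates: 1 − 0.95^6 = 26.5%. This shows how arbitrary the trigger is; it is not an error rate.

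**4. Precision, Aim 2 continuous scores.** Input: r = .50 between repeated measures (Sample Size and Power Calculations). Take unit variance and exchangeable correlation.

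- One visit, follow-up only: 1. Change from baseline: 2(1 − 0.5) = 1. Adjusted for baseline: 1 − 0.5² = 0.75. Reduction 25%; 315/0.75 = 420 unadjusted participants.
- Mean of four visits, follow-up only: (1 + 3 × 0.5)/4 = 0.625. Change from baseline: 0.625 + 1 − 2 × 0.5 = 0.625. Adjusted: 0.625 − 0.25 = 0.375. Ratio 0.60, reduction 40%; 315/0.60 = 525.

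The gain holds against either unadjusted approach. Entering baseline as one more repeated outcome with a free mean in each arm yields the change-from-baseline contrast and does not capture it. A common baseline mean does.

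If the unadjusted arm comparison has 80% power at 315, a covariate correlated 0.1 / 0.3 / 0.5 / 0.7 with the outcome gives 80.4 / 83.6 / 89.9 / 97.5%.

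**5. Precision, condomless sex.** Inputs: 0.55 v 0.40 at follow-up, 79% sexually active (0.79 × 315 ≈ 249). Simulated GEE (logit link), arm effect over four follow-ups, 500 runs per setting. The latent correlation between visits is assumed.

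| Latent correlation | Unadjusted | With baseline outcome |
|---|---|---|
| 0.3 | 95.6% | 95.0% |
| 0.5 | 89.0% | 93.0% |
| 0.7 | 82.4% | 93.2% |

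A weak covariate alone (latent correlation 0.1) moved power from 90.6% to 91.0%, within simulation error.

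**6. Arm by time.** For a linear time slope in complete data with an identity link, adding a covariate that is constant over time left the standard error of the interaction unchanged (0.0268 v 0.0268). With a logit link it moved power by 0 to 1.3 points.

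**7. Sparse outcomes.** PrEP uptake is assumed to be 2% at baseline and 4% in controls later: 0.04 × 105 = 4.2, about 4 control events. The baseline value carries almost no information, and the model can bear few added terms.

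**The case against.** Several stronger readings are tempting, and the documents do not support them.

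- *Covariates enter only on imbalance.* A reader might infer this from the equations section, but the sex rule is a second route that does not depend on balance.
- *The baseline outcome is not used.* The Aim 1 visit list omits baseline, but the objectives include it, the hypotheses concern improvement, and the power calculation starts from a baseline probability of 0.7. Its role is unclear, which is not the same as absent. The Aim 2 sentence omits nothing.
- *The rule inflates type I error.* This has not been shown. With 210 v 105, six independent covariates with joint correlation 0.1 to 0.5 with a continuous outcome, and 8,000 runs each, following the rule at p < 0.05 gave 4.1 to 5.2%. Taking the smaller of the adjusted and unadjusted p-values gave 4.5 to 5.9%.
- *Adjustment narrows every interval at no cost.* It does not. With a logit link, adjustment changes the estimand to a conditional odds ratio and need not shrink its standard error. It does nothing useful for the arm-by-time slope, and sparse outcomes pay for extra terms.
- *The trial is under-sized.* The power text claims no covariates, so any gain is a bonus.

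It is also fair to say that the documents give no prognostic strength for age or gender identity. The case for precision therefore rests mainly on the baseline outcome. What remains is that the model is not fixed in advance, the trigger is uninformative, and the sex rules conflict.

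**Conclusion.** The point stands in this form, as something that should be changed. Inclusion of covariates is discretionary and keyed to chance imbalance, a second rule for sex uses a different trigger, and the handling of the baseline outcome is ambiguous.

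The firm size is for the arm effect on Aim 2 continuous scores: 25% less variance at a single visit and 40% less for a four-visit mean. This rests on r = .50, exchangeable correlation and complete data. For condomless sex, power rises from about 82–89% to about 93% if the latent correlation is 0.7 to 0.5, with no gain at 0.3; those correlations are assumptions. Nothing material is gained for weak covariates, PrEP uptake or arm by time.

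**What to change.** 1. Delete the imbalance trigger. State that each Aim 1 and Aim 2 model carries the same short set whatever the observed balance: the baseline value of the outcome where it varies meaningfully, and gender identity. Age is optional.
2. State how baseline enters: as a covariate with the four follow-up visits as outcomes, or as a repeated outcome with a common baseline mean in both arms. Name the tested contrast, and note that the precision gain belongs to the arm contrast over the follow-up visits and not to a linear arm-by-time slope.
3. Replace the two sex rules with one: gender identity is always in the model, and any assessment of differential effect is a separate, pre-stated analysis.
4. For binary outcomes, report a standardised (marginal) risk difference so that adjustment does not turn the effect into a conditional odds ratio.
5. Say in advance that the PrEP and nPEP models carry few or no added covariates.
6. Keep the unadjusted model as a sensitivity analysis.

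The cost is plan wording, best settled before anyone sees outcomes by arm. Gender identity and age are in the baseline survey and a baseline assessment is already scheduled, so no new data are needed and the sample size does not change.
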